5.5. Subject Withdrawal / Termination Criteria

Whilst subjects are free to withdraw from the study at any time. All reasonable efforts should be made to retain the subjects for the 10-year duration of this study.

Study Site Discontinuation

A specific study site in this multicenter study may also warrant termination under the following conditions:

- non-compliance to Good Clinical Practice (GCP) or protocol
- major protocol deviations
- inaccurate or incomplete data
- unsafe or unethical practices
- safety or performance considerations
- investigator involuntarily discontinues participation in study

Documentation of withdrawn and lost to follow-up patients

Some actively enrolled subjects will not return for follow-up exams due to a variety of reasons. Study personnel will make all reasonable efforts to contact the subject and document the following contact attempts prior to declaring a subject to be lost to follow-up: the subject has been contacted according to the study sites policies, but no less than 2 documented phone contacts attempts and 1 letter without response. Copies of all attempts to reach the subjects per regular mail or email and/or the attempts to contact the subject via other means should be documented and kept with the subjects Case Report Form (CRF). A subject will be considered lost to follow-up if he/she does not appear for the scheduled study visit for 2 consecutive visits and study personnel are unable to contact the subject. For all cases (withdrawn and lost to follow-up), information will be obtained on the Study Termination Form, detailing circumstances leading to the withdrawal.

Sites will be requested to contact non-respondent patients using phone calls, regular mail, e-mail, certified letters or other means to urge patients to return to a clinic for follow-up or ascertain if a patient has moved.

6. Medical Devices

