3. STUDY DESIGN

This is a prospective, multicenter, observational study that is currently in the follow-up data collection phase. Five of the seven study sites that contributed data to the PMA cohort will participate in this PAS. The two sites that willnot participate in the PAS did not enroll any R3 Biolox delta Ceramic Acetabular System (DOD) PMA subjects, as such their data is not suitable for this PAS. The DOD treatment arm of the PMA Cohort included 137 DOD subjects.

Of the 137 DOD subjects included in the PMA Cohort, one died and one was revised by the 3-year follow-up interval. A total of 135 subjects are therefore eligible for this PAS study and all attempts will be made to continue follow-up on all subjects through the 10-year postoperative interval. Telephone follow-up for determination of device survival or revision status, and patient satisfaction in cases where subjects fail to return for follow-up visits will be conducted.

Document date: 01 Feb 2017; version 2.0 Confidential & Proprietary Page 9 of 25

Post-Approval Study of the R3 Biolox delta Ceramic Acetabular System – Europe	Protocol Number: R3H01/02/01/2017/Version2.0
	PMA Number P150030
	ADDENDUM Page: 10 of 25

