6.3. Telephone Follow-Up

If subjects are unable to return for follow-up visits to the investigator's office, they may be contacted by telephone to assess their status. Subjects will be asked whether the study device is in place or has been revised, and patient satisfaction will be assessed. This information will be recorded on the corresponding CRF.

Document date : 01 Feb 2017; version 2.0 Confidential & Proprietary Page 13 of 25

Post-Approval Study of the R3 Biolox delta Ceramic Acetabular System – Europe	Protocol Number: R3H01/02/01/2017/Version2.0				
	PMA Number P150030				
	ADDENDUM Page: 14 of 25				

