7.2. Conditions for Study Termination

All reasonable efforts should be made to retain the subjects for the 10-year duration of this study. If the subject has a revision of any component, the subject will be terminated from the study.

A. Voluntary Withdrawal

Study participation is voluntary and subjects may withdraw at any point during the study without giving their reason for doing so. A study termination form will be completed for all subjects who do not finish the study, to document the reason for the withdrawal in the CRF.

B. Lost to Follow-Up

Some actively enrolled subjects will not return for follow-up exams due to a variety of reasons. Study personnel will make a reasonable effort to contact the subject and document the following contact attempts prior to declaring a subject to be lost to follow-up: the subject has been contacted according to the study sites policies, but no less than 2 documented phone contacts and 1 certified letter without response. Copies of all attempts to reach the subjects per regular mail or email and/or the attempts to contact the subject via other means should be documented and such documentation should be kept with the subjects CRF. A subject will be considered lost to follow-up if he/she does not appear for the scheduled study visit for 2 consecutive visits and study personnel are unable to contact the subject.

C. Study Termination by Investigator/Sponsor

The Investigator may withdraw subjects from the study for many reasons, including but not limited to the following:

- subject noncompliance to study schematic
- subject lost to follow-up

The Investigator **should** withdraw subjects from the study:

- in case any component of the original hardware is revised/exchanged
- if the Investigator or the Sponsor stops the study for any reason

For each case, information will be obtained on the Study Termination Form, detailing circumstances leading to the withdrawal.

D. Study Site Discontinuation

Document date : 01 Feb 2017; version 2.0 Confidential & Proprietary Page 14 of 25

Post-Approval Study of the R3 Biolox delta Ceramic Acetabular System – Europe	Protocol Number: R3H01/02/01/2017/Version2.0			
	PMA Number P150030			
	ADDENDUM Page: 15 of 25			

A specific study site in this multicenter study may also warrant termination under the following conditions:

- non-compliance to Good Clinical Practice (GCP) or protocol
- major protocol deviations
- inaccurate or incomplete data
- unsafe or unethical practices

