9.2. Sample size

The DOD cohort of the PMA consisted of 137 DOD subjects. The sample size is fixed, based on the number of subjects enrolled in the European Cohort Study. Of the 137 DOD subjects included in the PMA Cohort, one died and one was revised by the 3-year follow-up interval. Thus, a total of 135 subjects are eligible for this PAS study and all attempts will be made to continue follow-up on all subjects throughout 10 years, including telephone follow-up for determination of device survival or revision status in cases where subjects fail to return for follow-up visits.

Document date : 01 Feb 2017; version 2.0 Confidential & Proprietary Page 19 of 25

Post-Approval Study of the R3 Biolox delta Ceramic Acetabular System – Europe	Protocol Number: R3H01/02/01/2017/Version2.0	
	PMA Number P150030	
	ADDENDUM Page: 20 of 25	

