Patient address unknown	Patient is non-compliant with study require	ements				
	Other, please specify:					
Contact the subject by telephone and confirm the information below. If during the discussion Serious Adverse Events are revealed, complete the Adverse Event and Serious Adverse Event case report forms. Record telephone contact in the medical notes.						
Telephone Follow-up						
Unable to contact subject by p	hone during the visit window (No furthe	er response required)				
Ask the following questions an						
1. Has any component of yo	our Smith & Nephew modular hip been i	removed since your last visit?				
Yes No						
Complete Adverse	Event Case Report Form					
2. Have you had any proble	ems with the study hip since the last visit	t to the clinic?				
Yes No						
Complete Adverse	e Event Case Report Form					
3. Do you expect to have the	e study device removed during the next	year?				
Yes No						
Request subject to	contact study coordinator following the ren	noval of device				
4. How satisfied are you wit	h your hip replacement?					
☐ Very satisfied ☐ S	Somewhat satisfied Somewhat dissatis	fied Very dissatisfied				
5. If you had to make the de	ecision again to undergo your hip replace	ement surgery, would you do it again?				
Yes No						
Investigator's Signature:		Date: Month Year				

Plate # 300

smith&nephew

Adverse Event

Project No:			R3
Study Patient No:			

Please complete ONE event form per complica Number each event sequentially beginning wit	h "01" Date of Onset: L. L. L. L. L. L. L. L. L. L. L. L. L.
Event No:	Day Month Year
Adverse Event	
Event / Diagnosis please specify: Severity (Tick one box only) mild moderate severe Serious (Tick one box only) no yes Involves operated side (Tick one box only) no yes not applicable	Outcome of complication (Tick one box only) resolved ongoing / unresolved death, date prosthesis in situ at date of death no, latest date known Removal or revision of component(s), date:
Relationship to study device (Tick one box only) definitely related	Day Month Year
probably related possibly related not related Relationship to study procedure (Tick one box only) definitely related probably related possibly related not related reatment none medication/orthotics	Components removed / revised femoral head femoral stem acetabular cup taper sleeve acetabular liner Hospital (inpatient or outpatient) / Readmission required? no yes, date of readmission:
Investigator's Signature:	Date: Day Month Year

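### Addendum 7.2.C permits withdrawal of a reachable subject for missing visits, which conflicts with the telephone follow-up that the 10-year survivorship endpoint relies on

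*Combined protocol and SAP*

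**What the plan says.** Addendum 7.2.C opens its discretionary list with "The Investigator may withdraw subjects from the study for many reasons, including but not limited to the following". The first reason given is "subject noncompliance to study schematic"; loss to follow-up is a separate entry. The schematic (Addendum 6.1, Table 1) consists of the mHHS, radiographs and adverse event assessment at 5, 7 and 10 years, so a missed visit is noncompliance with it. No threshold, definition or prior telephone step is attached.

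Loss to follow-up is defined much more strictly in 7.2.B: the subject "does not appear for the scheduled study visit for 2 consecutive visits and study personnel are unable to contact the subject", after documented calls and a certified letter.

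Other sections point the other way. Addendum 9.2 promises that "all attempts will be made to continue follow-up on all subjects throughout 10 years". Addendum 3 says that telephone determination of device status "in cases where subjects fail to return for follow-up visits will be conducted". SAP 3.1 and 3.3 repeat both commitments. The Missed Visit/Telephone Follow-up form, restricted to subjects who remain on study, offers "Patient is non-compliant with study" requirements as a reason for a missed visit and then asks whether any component has been removed.

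Addendum 6.3 is weaker: for subjects unable to return, "they may be contacted by telephone to assess their status". SAP 3.2 and main protocol 7.5 use the same permissive wording.

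Addendum 9.1 and SAP 7.1 censor anyone without a removal at the point when data were last collected. Neither makes an exception for withdrawal by the investigator.

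**The concern.** A subject who stops attending but still answers the telephone can supply everything the primary endpoint needs. Under 7.2.C that subject can be withdrawn, after which the form that asks the removal question no longer applies. Device status at the remaining intervals is then lost by choice, not by necessity.

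Kaplan-Meier treats the withdrawn subject as having the same later revision risk as those who stay. If non-attendance goes with dissatisfaction, or with revision at another hospital, the estimate is too favourable. If it does not, the cost is lost information in a fixed cohort that cannot be enlarged. Voluntary withdrawal is protected separately in 7.2.A, so the noncompliance ground is not needed to respect a subject's wish to leave.

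**Working it through.** **The texts side by side**

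| Situation | Text | Consequence |
|---|---|---|
| Fails to return | Addendum 3 and 9.2; SAP 3.1 and 3.3 | Telephone status check is committed to |
| Unable to return | Addendum 6.3; SAP 3.2; main protocol 7.5 | Telephone call is optional |
| Non-compliant, visit missed | Missed-visit form | Subject stays on study; removal question asked |
| Non-compliant with schematic | Addendum 7.2.C | Investigator may withdraw |
| Two consecutive visits missed and unreachable | Addendum 7.2.B | Lost to follow-up |

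The third and fourth rows describe the same subject with opposite outcomes. Nothing says which text prevails.

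**Inputs from the documents**

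- PAS cohort (Addendum 3, 9.2): 137 − 1 death − 1 revision = 135, as stated.
- Three-year survivorship (Addendum 2.1, SAP 3.5.1): S3 = 136/137 = 0.9927, which reproduces the stated 99.3%.
- Censoring rule (Addendum 9.1, SAP 7.1): follow-up before withdrawal stays in the estimate.

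**Assumptions, none of them in the documents**

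- Ten-year failure in attenders, p: 5% or 10%.
- Fraction of the 135 who stop attending and are withdrawn, f: 10% or 20% (about 14 or 27 subjects).
- Their hazard relative to attenders, R: 2 or 3.
- Constant hazard h from year 3 to year 10, and withdrawal at year 5.

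**Formulas**

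- Hazard: S3·exp(−7h) = 1 − p. For p = 5%, exp(−7h) = 0.95/0.9927 = 0.9570 and h = 0.00628 per year. For p = 10%, h = 0.01400.
- True survivorship = S3·[(1−f)·exp(−7h) + f·exp(−7Rh)].
- Expected Kaplan-Meier = S3·[(1−f)·exp(−2h) + f·exp(−2Rh)]·exp(−5h). Withdrawn subjects count to year 5; only attenders inform years 5 to 10.

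**Worked case: p = 5%, f = 20%, R = 3**

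- True: 0.9927 × (0.8 × 0.9570 + 0.2 × 0.8764) = 0.9340.
- Kaplan-Meier: 0.9927 × (0.8 × 0.9875 + 0.2 × 0.9630) × 0.9691 = 0.9453.
- Overstatement: 1.13 points.

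**All cases, withdrawal at 5 years (%)**

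| p | f | R | True | Kaplan-Meier | Overstatement (points) |
|---|---|---|---|---|---|
| 5 | 10 | 2 | 94.59 | 94.88 | 0.29 |
| 5 | 10 | 3 | 94.20 | 94.76 | 0.56 |
| 5 | 20 | 2 | 94.18 | 94.76 | 0.58 |
| 5 | 20 | 3 | 93.40 | 94.53 | 1.13 |
| 10 | 10 | 2 | 89.16 | 89.75 | 0.59 |
| 10 | 10 | 3 | 88.40 | 89.51 | 1.11 |
| 10 | 20 | 2 | 88.32 | 89.50 | 1.18 |
| 10 | 20 | 3 | 86.80 | 89.02 | 2.22 |

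With withdrawal at 7 years and p = 5%, the range falls to 0.17 to 0.67 points. At R = 1 it is zero throughout.

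**Effect on the SAP's missing-as-failure analysis**

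If withdrawn subjects count as missing, which SAP 4.4 does not define for a censored endpoint, the result is (1−f)(1−p). For p = 5% that is 0.9 × 0.95 = 85.5% or 0.8 × 0.95 = 76.0%. The bound is then driven by avoidable withdrawals.

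**The case against.** The withdrawal is discretionary, and Section 7.2 itself begins with the same retention statement as main protocol 5.5: "All reasonable efforts should be made to retain the subjects for the 10-year duration of this study". A site that honours the whole addendum would make the telephone call required by Addendum 3. That is a fair reading of intent, and it rules out saying that the plan directs sites to drop non-attenders. It does not remove the permission, and a call at one missed visit does not supply status at later intervals once the subject is off study. The Study Termination Form is not in the text available to me, so I cannot say whether it records device status at exit.

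The SAP also gives some protection. Section 4.4 plans a missing-as-failure analysis and a tipping-point analysis. Section 6 subtracts only deaths and revisions from the expected number, so withdrawn subjects stay in the follow-up-rate denominator, and discontinuation reasons are tabulated. Withdrawals would therefore be visible, but the lost status would not be recovered.

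The bias is modest beside sampling error: for 95% survivorship in 135 subjects, ignoring censoring, the 95% half-width is 1.96 × √(0.95 × 0.05/135) = 3.7 points.

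Three stronger readings are tempting but unsupported:

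- **That DOD subjects can be withdrawn where subjects in the other arms cannot.** Main protocol 5.5 lists no investigator grounds for withdrawing individual subjects, but it prohibits none and refers generally to withdrawn cases. Silence is not a prohibition.
- **That the bias is f·p·(R−1), or 0.5 to 2.0 points at 5% failure and 1 to 4 at 10%.** That treats withdrawn subjects as contributing nothing from surgery onward. All 135 had passed 3 years unrevised, and their follow-up to withdrawal is kept.
- **That non-attenders do carry a higher revision risk.** The documents give no evidence either way.

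**Conclusion.** The point holds as a conflict between passages that bears on the primary endpoint. Addendum 7.2.C permits withdrawal of a reachable subject for missing visits; the telephone commitments and the missed-visit form imply that the subject stays; Addendum 6.3 and SAP 3.2 leave the call optional.

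Under the stated assumptions, the 10-year estimate is about 0.3 to 1.1 points too high at 5% failure in attenders, or 0.6 to 2.2 points at 10%. The bias shrinks with later withdrawal and vanishes at equal risk, where the loss is precision only. The conflict is certain from the text. The size is illustrative, because the withdrawn fraction, the relative risk and the failure rate are all assumed. The PAS has no hypothesis test, so no formal conclusion turns on it, but the survivorship estimate is the main output and the missing information is cheap to obtain.

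**What to change.** 1. In Addendum 7.2.C, state that missed visits, mHHS assessments or radiographs are protocol deviations and are not by themselves a reason for withdrawal, and remove the noncompliance entry accordingly. Deleting the entry alone would achieve nothing, because the list is expressly open-ended; the added sentence does the work.
2. State that such subjects stay on study, with device status and any removal date collected by telephone at 5, 7 and 10 years unless consent is withdrawn.
3. In Addendum 6.3 and SAP 3.2, change the trigger from being unable to return to failing to return, and make the call mandatory, to match Addendum 3 and 9.2. Make the same change in main protocol 7.5 for consistency.

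The cost is a short amendment, a few extra calls on a form that already exists, and more listed visit deviations. Missed visits are already deviations under Addendum 12 and SAP 9, and according to Addendum 7.1 the signed consent already covers follow-up to 10 years.

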8. SAFETY REPORTING

All adverse events, regardless of their relationship to the study device, occurring from the time of study device implantation through to study completion should be recorded on the appropriate CRFs and reported as below.

8.1. Definitions for safety reporting

A. Adverse Event (AE)

An AE is any untoward medical occurrence, unintended disease or injury, or untoward clinical signs (including abnormal laboratory findings) in subjects, users or other persons, whether or not related to the study medical device.

B. Serious Adverse Event (SAE)

A SAE is any adverse event that:

- resulted to death,
- was life threatening (at the time of the event); or
- resulted in hospitalization (initial or prolonged); or
- resulted in a disability or permanent damage (a significant, persistent or permanent change, impairment, damage or disruption in the patient's body function/structure, physical activities and/or quality of life);or
- resulted in a congenital anomaly or birth defect; or
- required medical or surgical intervention to preclude permanent impairment of a body function or prevent permanent damage to a body structure; or
- does not fit the other outcomes above, but may jeopardize the subject and may require medical or surgical intervention (treatment) to prevent one of the other outcomes.

Planned hospitalization for a pre-existing condition, or a procedure required by the protocol, without serious deterioration in health, is not considered a serious adverse event.

C. Unanticipated Serious Adverse Device Effect (USADE)

Any serious adverse effect on health or safety or any life-threatening problem or death caused by, or associated with, a device, if that effect, problem, or death was not previously identified in nature, severity, or degree of incidence in the investigational plan or application (including a supplementary plan or application), or any other unanticipated serious problem associated with the device that relates to the rights, safety, or welfare of subjects.

The Investigator will assess and categorize AEs as mild, moderate or severe based on the following definitions:

Mild: the subject is aware of the sign or symptom, but finds it easily tolerated. The event is of little concern
to the subject and/or little clinical significance. The event is not expected to have any effect on the
subject's overall health or wellbeing.

Document date : 01 Feb 2017; version 2.0 Confidential & Proprietary Page 16 of 25

Post-Approval Study of the R3 Biolox delta Ceramic Acetabular System – Europe	Protocol Number: R3H01/02/01/2017/Version2.0	
	PMA Number P150030	
	ADDENDUM Page: 17 of 25	

- Moderate: the subject has discomfort enough to cause interference with or change in usual activities. The
 event is of some concern to the subject's health or wellbeing and may require medical intervention and/or
 close follow-up.
- Severe: the adverse event interferes considerably with the subject's usual activities. The event is of
 definite concern to the subject and/or poses substantial risk to the subject's health or well-being. The
 event is likely to require medical intervention and/or close follow-up and may be incapacitating orlife
 threatening. Hospitalization and treatment may be required.

The Investigator is responsible for assessing the relationship of the AE to the study device and study procedure based on the following definitions:

- Unrelated: the event is clearly not related to the study device or study procedure
- Possible: the event may or may not be related to the study device or study procedure. Arelationship cannot be ruled out.
- Probable: the event is likely related to the study device or study procedure. A relationship cannot be ruled out.
- Definite: the event is clearly related to the study device or study procedure.

Document date: 01 Feb 2017; version 2.0 Confidential & Proprietary Page 17 of 25

Post-Approval Study of the R3 Biolox delta Ceramic Acetabular System – Europe	Protocol Number: R3H01/02/01/2017/Version2.0	
	PMA Number P150030	
	ADDENDUM Page: 18 of 25	

D. Reoperation and Revisions

A reoperation is any surgical procedure of the study hip. A revision is a surgical procedure of the study hip where one or more of the study components are removed and replaced with new implants.

All reoperations and study component revisions should be documented on the Adverse EventCRF.

8.2. Safety: Investigator's Responsibilities

All reportable adverse events that occur during this follow-up phase should be fully documented in the research record by the Investigator including the onset date, complete description of the event, severity, duration, action taken, and outcome. The event should be documented on the Adverse Event case report form. The investigator will be responsible for notifying the reviewing Ethics Committee, and if applicable other authorities, of anyreportable adverse events according to local regulations.

Adverse events which are possibly, probably, or definitely related to the device must be reported promptly to the sponsor. Adverse events which are unanticipated (UADE) must be reported to the sponsor by telephone or by email as soon as possible, and the completed adverse event CRF must be faxed to the Sponsor within 10 working days of gaining knowledge of the event together with a cover letter describing the event and detailing the medical history.

The investigator shall also supply a copy of the completed adverse event investigation form, together with a cover letter describing the event and detailing the medical history to the Ethics Committee. The investigator will also provide any relevant follow-up information and the outcome of the event as soon as possible.

